7. PLANNED ANALYSIS

For End-Of-Text (EoT) tables, the set of summary statistics is: N / Mean / SD / Min / Median / Max. In descriptive statistics tables, mean and median will be rounded to one additional digit than the raw individual value. SD will be rounded to one additional digit than the mean.

For tables that are provided for endpoints with some extreme data, median, quartiles and percentiles should be preferred to mean, standard deviation, minimum and maximum.

Tabulations of frequencies for categorical data will include all possible categories and will display the number of observations in a category as well as the percentage (%) relative to the respective treatment group (unless otherwise specified, all subjects in the respective subject set whether they have non-missing values or not).

The precision for percentages should be one decimal point, unless the denominator is smaller than 100 (in all treatment columns), in which case percentages are given in integer numbers. The category missing will be displayed only if there are actually missing values.

7.1 DEMOGRAPHIC AND OTHER BASELINE CHARACTERISTICS

Only descriptive statistics are planned for this section of the report.

7.2 CONCOMITANT DISEASES AND MEDICATION

Only descriptive statistics are planned for this section of the report.

7.2.1 Baseline conditions

A summary of baseline conditions will be provided by treatment group, System Organ Class (SOC) and Preferred Term (PT). SOC will be sorted according to the standard sort order specified by EMA and PT by descending frequency over both treatment arms.

7.2.2 Concomitant therapies

Concomitant therapies will be described over several study periods, listed below.

- Previous therapies will be defined as treatments with an end date before baseline.
- Baseline therapies will be defined as treatments with a start date before baseline and a stop date after or on baseline.
- On-treatment therapies will be defined as treatments with a start date during the nintedanib treatment period defined in Section 6.1.
- Post-study drug discontinuation concomitant therapies are defined as treatments with a start date during the residual effect, post-treatment or post-study period defined in Section 6.1.

A summary of all on-treatment concomitant therapies (including baseline CTs) will be provided by treatment group, ATC3 codes and Preferred Name (PN) (sorted by alphabetical ATC class and decreasing frequency of preferred names in Nintedanib treatment arm within ATC class).

Relevant groups of therapies have been defined as Special Search Categories (SSC) or Standardised Drug Groupings (SDG).

A summary of baseline concomitant therapies, on-treatment concomitant therapies will also be performed by Special Search Category (SSC) or Standardised Drug Groupings (SDG) and Preferred Name (PN) (sorted by alphabetical SSC or SDG and decreasing frequency of preferred names within SSC or SDG).

Finally, specific tables for selected concomitant treatments that were restricted during the study will be provided (by PN):

- All on-treatment concomitant therapies (including baseline CTs)
- All concomitant therapies (including baseline CTs, on-treatment CTs)

~~Non drug therapies will be included as coded items using the current Medical Dictionary for Regulatory Activities (MedDRA) version in use at BI at the time of database lock. They will be summarised by MedDRA system organ class (SOC) and Preferred Term. The CTR table will show the counts of patients with a condition in each SOC present (SOC sorted by standard European Medicines Agency (EMA) order) and then the conditions (preferred terms) under that SOC in descending order of overall prevalence.~~

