4.2.2 Restrictions

4.2.2.1 Restrictions on concomitant treatment

The following drugs must not be taken within 8 weeks of visit 1:

- Pirfenidone
- Any other experimental IPF therapy.

The following therapies are not allowed during the entire treatment period (Visit 2-7). In case any of the following is medically indicated during the course of the trial a 4 week wash-out of nintedanib should be observed before their use:

Fibrinolysis, full-dose therapeutic anticoagulation (e.g. vitamin K antagonists, dabigatran, heparin, hirudin etc), or high dose antiplatelet therapy.

The following drugs are not allowed during the study treatment except in case of acute exacerbation of IPF or in case of deterioration at the discretion of the investigator (see section 4.2.2.2):

- Azathioprine, cyclophosphamide and cyclosporine A must not be taken within 8 weeks of visit 1.
- N-Acetyl Cysteine (NAC). Must not be taken within 2 weeks of visit 1.
- Prednisone at > 15 mg /day (or > 30 mg every 2 days or equivalent dose of other oral corticosteroid) must not be taken within 2 weeks of visit 1.

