6. GENERAL ANALYSIS DEFINITIONS

6.1 TREATMENT(S)

For treatment specifications, see Section 4 of the CTP.

The following trial periods will be defined with respect to efficacy analyses: Screening, Post-randomization, Treatment, Post-treatment.

- Screening: from first informed consent to randomization
- Post-randomization: from randomization to day of first pulmonary rehabilitation (for those randomized to Pulmonary Rehabilitation Treatment group)
- Treatment:
 - For patients randomized to the Non-Pulmonary Rehabilitation Treatment group: from randomization to the visit 7 end-of-trial visit
 - For patients randomized to the Pulmonary Rehabilitation Treatment group: from first day of pulmonary rehabilitation to the visit 7 end-of-trial visit
- Post-treatment: after the visit 7 end-of-trial visit

Efficacy analyses is independent of nintedanib usage: any dose interruption or discontinuation has no effect on the efficacy analyses. Efficacy analyses will be done on the Post-randomization and Treatment Periods.

The following trial periods will be defined with respect to safety analyses:

Note: the last day of each of the following periods is excluded.

- Screening: from first informed consent to randomization
- Post-randomization: from randomization to day of first Nintedanib drug intake on/after randomization. This period only exists if Nintedanib first drug intake on/after randomization occurred at least 1 day after randomization.
- Treatment: from first Nintedanib drug intake on/after randomization (or re-start of nintedanib if interruption) to last Nintedanib drug intake (or the day before start date of interruption if interruption) plus one day.
- Off-treatment^a: From the start date of Nintedanib interruption to re-start of Nintedanib treatment.
- Residual-effect^a: From the last Nintedanib drug intake plus one day to last Nintedanib trial drug intake plus 28 days plus one day.
- Post-treatment^a: From last trial drug intake plus 29 days. Note, this period is only created if last Nintedanib intake plus 29 days took place before trial completion.
- Post-study: from the latest of last trial drug intake plus 29 days or date of trial completion plus 1 day

^a Note: This period is optional insofar as it does not necessarily exist for all patients.

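### SAP 7.2.2 ties on-treatment concomitant therapy to nintedanib intake, so therapies started off nintedanib are unclassified or not clearly tabulated by arm

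*SAP*

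**What the plan says.** SAP 6.1 defines two sets of periods. The efficacy set follows the randomised comparison, and the SAP states there that "any dose interruption or discontinuation has no effect on the efficacy analyses". The safety set follows nintedanib intake:

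- Treatment runs from the first intake on or after randomisation, or from a re-start, "to last Nintedanib drug intake (or the day before start date of interruption if interruption) plus one day".
- An optional off-treatment period runs "From the start date of Nintedanib interruption to re-start of Nintedanib treatment".
- A short period can precede the first intake: "Post-randomization: from randomization to day of first Nintedanib drug intake on/after randomization".
- Residual-effect, post-treatment and post-study periods follow the last intake.
- On boundaries: "Note: the last day of each of the following periods is excluded".

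SAP 7.2.2 then defines four classes of therapy. Previous therapies end before baseline. Baseline therapies start before baseline and stop on or after it. For the third class, "On-treatment therapies will be defined as treatments with a start date during the nintedanib treatment period defined in Section 6.1". The fourth, after study-drug discontinuation, covers "treatments with a start date during the residual effect, post-treatment or post-study period defined in Section 6.1".

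The planned tables are a summary by treatment group, ATC3 code and preferred name (on-treatment plus baseline), a summary by SSC or SDG (baseline and on-treatment), and two tables for selected restricted treatments. The first restricted table covers on-treatment plus baseline. The second is headed as covering all concomitant therapies, with a bracket naming baseline and on-treatment.

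Protocol 4.2.2.1 says that if fibrinolysis, full-dose anticoagulation or high-dose antiplatelet therapy becomes medically indicated, "a 4 week wash-out of nintedanib should be observed before their use".

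**The concern.** Concomitant-therapy tables let a reader judge whether the arms differed in other treatments that could move 6MWD, FVC or quality of life. Here the arms differ by rehabilitation, yet the tables count new therapies only while nintedanib is being taken. A patient who interrupts or stops nintedanib keeps contributing efficacy data up to Visit 7, but a drug started during that time drops out of the main therapy summaries.

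Protocol 4.2.2.2 allows high-dose prednisone, azathioprine, cyclophosphamide, cyclosporine A and NAC to be started for an acute exacerbation or deterioration. If nintedanib is interrupted at that time, the rescue drug is in no class. Because SAP sections 4, 7.4.1 and 7.5.2 now limit efficacy to descriptive statistics, no model adjustment is planned. The by-arm therapy tables are then one of the few places where unequal rescue use would show.

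**Working it through.** The documents state no figure on this point, so there is none to reproduce. The check sets the SAP 6.1 safety periods against the SAP 7.2.2 classes and the planned tables.

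**Step 1: periods, classes and tables**

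| Therapy starts in | Class in SAP 7.2.2 | Named in ATC3 and SSC/SDG summaries? |
|---|---|---|
| Post-randomisation, before first intake | none | no |
| Nintedanib treatment | on-treatment | yes |
| Off-treatment (interruption) | none | no |
| Residual-effect, post-treatment, post-study | post-discontinuation | no |

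**Step 2: the boundary.** With an interruption from day *i*, treatment ends at (*i* − 1) + 1 = *i*. The last day is excluded, so day *i* is not a treatment day and the whole interruption lies outside treatment.

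**Step 3: an illustrative patient.** These days are assumed. Randomised and dosed on day 1, interruption from day 40, re-start on day 68, last intake on day 120, trial completion on day 169.

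- On-treatment: days 1–39 and 68–120, 39 + 53 = 92 days.
- No class: days 40–67, 68 − 40 = 28 days.
- Post-discontinuation: residual-effect days 121–148 (28) plus post-treatment days 149–169 (21), 28 + 21 = 49 days.
- Check: 92 + 28 + 49 = 169.

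For this patient 28/169 = 17% of possible start days have no class. A further 49/169 = 29% have a class that the ATC3 and SSC/SDG summaries do not name. If the first intake after randomisation is on day 5 instead, days 1–4 also have no class and on-treatment falls to 88 days (88 + 28 + 49 + 4 = 169). With no interruption, no delay and no stop, both shares are zero.

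**Step 4: the wash-out in protocol 4.2.2.1.**

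- Last dose on day 39, interruption from day 40, re-start on day 75. A drug started after 28 days, on day 39 + 28 = 67, is in off-treatment and has no class.
- Permanent stop with last intake on day 120. A drug started 28 or 29 days later, on day 148 or 149, is in the post-discontinuation class.

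In both cases an antithrombotic started after the wash-out, with nintedanib still withheld, falls outside on-treatment.

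**Step 5: the restricted-treatment tables.** If the bracket in the second table is a complete list, that table repeats the first. If it only gives examples, the table may include starts off nintedanib. The text does not say which.

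**The case against.** The strongest reply is that SAP 7.2.2 opens by promising a description over all the listed periods, post-discontinuation included, and that the second restricted-treatment table, read naturally, adds whatever the first leaves out. A reader might infer that drugs started after a permanent stop have no planned table at all. The documents do not support that for the selected restricted drugs, where the wording is ambiguous. The omission stands for the ATC3 and SSC/SDG summaries, which name only baseline and on-treatment therapies.

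SAP 7.8.1 treats off-treatment as a label in the adverse-event listings, and it could be meant the same way here. That section concerns adverse events only, and SAP 7.2.2 has no matching rule for therapies.

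The data are not lost. Protocol 7.3 lists all individual data. Deviation D1 in SAP 6.2 covers prohibited therapies in the treatment phase and is not worded by nintedanib intake. This limits the harm. However, a listing gives no comparison between arms, and D1 need not capture the rescue drugs that protocol 4.2.2.2 permits.

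The post-randomisation gap is nearly empty, since protocol 3.3.2 requires nintedanib to have been started by the day of randomisation.

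Three further inferences go beyond the documents:

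- **All restricted drugs conflict with the wash-out.** It applies only to the antithrombotic group. Steroids, immunosuppressants and NAC started while the patient takes nintedanib are counted as on-treatment.
- **The sickest patients are the ones missed, so the arms look falsely balanced.** This is possible, but nothing in the documents shows it.
- **A count of affected patients can be had from the planned 145 per arm.** The documents give no interruption rate and no rate of new therapies among those who interrupt, and the trial was terminated.

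**Conclusion.** The point holds as a defect in classification and tabulation. Read as written, SAP 7.2.2 leaves therapies started during an interruption, or in the rare post-randomisation gap, without a class. It also leaves therapies started after a permanent stop out of the ATC3 and SSC/SDG summaries. Coverage of the second restricted-treatment table is unclear. A rule tied to background medication therefore undercounts new therapies in a trial randomised to rehabilitation, while the same patients' efficacy data stay in.

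The effect is limited to descriptive tables. No hypothesis test or planned model depends on them. For an individual patient the unclassified time equals the length of the interruption plus any delay to first intake; the 17% and 29% shares belong only to the assumed patient. The number of patients affected and any imbalance between arms cannot be derived from the documents. The conclusion assumes that the class definitions are applied literally and that the nintedanib period in SAP 7.2.2 is the safety treatment period of SAP 6.1. It is worth correcting before the tables are produced.

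**What to change.** In SAP 7.2.2, define an on-study class: any therapy with a start date from randomisation to Visit 7 or trial completion, regardless of nintedanib intake. Use it for the ATC3, SSC/SDG and restricted-treatment tables by randomised arm, and carry on/off-nintedanib status as a flag in the listing.

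If the existing classes are kept, the minimum is to:

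- assign off-treatment and post-randomisation starts to a class that is tabulated;
- add post-discontinuation starts to the ATC3 and SSC/SDG summaries;
- state that the second restricted-treatment table includes all of these.

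The cost is one definition, minor reprogramming on data already collected, and slightly longer tables. Nothing changes in the conduct of the trial or the care of patients.

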7.3 TREATMENT COMPLIANCE

Only descriptive statistics are planned for this section of the report.

7.4 PRIMARY ENDPOINT

7.4.1 Primary analysis of the primary endpoint

The primary analysis will be conducted on the RS set. Only descriptive statistics are planned for this section of the report.~~The analysis of the primary endpoint will be conducted in accordance with Section 7.3.1 of the CTP.~~

7.4.2 Sensitivity analysis of the primary endpoint

~~Multiple imputation will be used to handle missing data as a sensitivity analysis using the RS set. All variables included in the analysis model will be included in the imputation model. In addition, after exploring the missing data mechanism and observed measurements on the blinded data additional variables may be included in the imputation model.~~

~~When there is no missing baseline information in the imputation model, regression method will be used. When there is missing baseline information in the imputation model, MCMC method will be used. For each imputed complete dataset, the primary analysis model will be~~

used for the analysis. The results will be pooled following the standard multiple imputation procedure.

7.5 SECONDARY ENDPOINTS

7.5.1 Key secondary endpoint

This section is not applicable as no key secondary endpoint has been specified in the CTP.

7.5.2 (Other) Secondary endpoints

The 12-week and 24-week secondary endpoints will be analyzed on the RS set. Only descriptive statistics are planned for this section of the report. ~~The analyses of these secondary endpoints will be conducted in accordance with Section 7.3.2 of the CTP.~~

~~The 24-week secondary endpoints will be analyzed on the RS set. The analysis of these secondary endpoints will be conducted in accordance with Section 7.3.2 of the CTP. In the event of non-convergence, the following methods will be attempted (in order) to overcome it:~~

- ~~1. Add the 'singular=1e-10' option in the model statement. This raises the threshold at which columns are declared linearly dependent (from typically 1e-12).~~
- ~~2. Set 'maxiter=100' in the Proc Mixed statement. This increases the number of convergence iterations used from a default of 50.~~
- ~~3. Set 'scoring=4' to specify use of the Fisher scoring algorithm in the first 4 iterations.~~
- ~~4. Include the statement 'performance nothread'—this removes multi-threading from the calculations.~~

[figure not shown]
Secondary endpoints with FVC % predicted will be derived using the following formula:

[figure not shown]
$$\text{FVC \% Predicted} = 100 \times \frac{\text{FVC [L]}}{\text{FVC Predicted [L]}}$$

Where,

$$\text{FVC Predicted [L]} = \begin{cases} 5.76 \times \text{Height(m)} - 0.026 \times \text{Age} - 4.34 & \text{if Male} \\ 4.43 \times \text{Height(m)} - 0.026 \times \text{Age} - 2.89 & \text{if Female} \end{cases}$$

Age will be as collected at Visit 1.

7.7 EXTENT OF EXPOSURE

The data will be analysed on the RS. A summary table showing the duration on pulmonary rehabilitation (both mean and frequency, see Section 5.4.3).

A table displaying the disposition of patients and the conclusion of patients' participation, and a table displaying the primary reason for non-inclusion/randomization will be provided.

7.8 SAFETY ANALYSIS

All safety analyses will be performed on the RS. The analysis will be performed as defined in the CTP. That is, analysis of adverse events will be restricted to nintedanib-related serious adverse events, nintedanib-non-related serious adverse events and events of special interest. Adverse events of special interest include DILI and GI Perforation.

7.8.1 Adverse Events

The analyses of AEs will be descriptive in nature and will be based on BI standards (11). No hypothesis testing is planned. All analyses of AEs will be based on the number of subjects with AEs and NOT on the number of AEs.

For analysis, multiple AE occurrence data on the CRF will be collapsed into an AE event provided that all of the following applies:

- All AE attributes are identical (LLT, intensity, action taken, therapy required, seriousness, reason for seriousness, relationship [investigator defined drug-relatedness], outcome, AE of special interest)
- The occurrences were time-overlapping or time-adjacent (time-adjacency of 2 occurrences is given if the second occurrence started on the same day or on the day after the end of the first occurrence)

For further details on summarization of AE data, please refer to the guideline "Analysis and Presentation of Adverse Event Data from Clinical Trials" (11).

The analysis of adverse events will be based on the concept of treatment emergent adverse events. That means that all adverse events occurring between first nintedanib intake on/after randomization till 28 days after last nintedanib intake will be assigned to the treatment period. All adverse events occurring before first nintedanib intake will be assigned to 'screening' or 'post-randomisation' and all adverse events occurring after last nintedanib intake will be assigned to 'residual effect', 'post-treatment' or 'post-study' (for listings only). Also, all adverse events occurring between the start of an interruption and the end of interruption will be assigned to 'off-treatment' period in the listings. For details on the treatment definition, see Section 6.1.

According to ICH E3 (10), AEs classified as 'other significant' needs to be reported and will include those non-serious and non-significant AEs with (i) 'action taken = discontinuation' or 'action taken = reduced', or (ii) marked haematological and other lab abnormalities or lead to

significant concomitant therapy as identified by the Clinical Monitor/Investigator at a MQRM.

An overall summary of adverse events will be presented. The frequency of subjects with AEs will be summarised by treatment, primary system organ class and PT (mention MedDRA levels to be displayed in the tables). Separate tables will be provided for subjects with other significant adverse events according to ICH E3 (10), for subjects with significant non-serious adverse events (only if these are defined for the project) and for subjects with serious adverse events (SAEs).

The system organ classes will be sorted by default alphabetically, PTs will be sorted by frequency (within SOC). Customized sorting orders may also be used based on trial needs, e.g. SOC sorted by frequency.

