3. DESCRIPTION OF DESIGN AND TRIAL POPULATION

3.1 OVERALL TRIAL DESIGN AND PLAN

This is a Phase IV, multi-centre, prospective, randomised, open label clinical trial to investigate the effect of pulmonary rehabilitation in patients with IPF currently treated with nintedanib at a dose of 150 mg bid for up to 30 months.

A total of approximately 290 patients with confirmed IPF diagnosis, already using nintedanib will be randomised, 145 in active arm and 145 in the control group. [REDACTED]

After a screening visit, if the patient complies with all inclusion and exclusion criteria and provides informed consent, randomisation will be performed by phone or Internet, using an Interactive phone/web Response System (IRT). Patients will then enter the treatment phase for 24 weeks. The treatment phase consists of 12 weeks of pulmonary rehabilitation for those patients randomized to that arm, to take place during the first 12 weeks of the treatment phase.

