6.2.2 Treatment period(s)

Treatment phase will be a 24 week period, beginning at visit 2.

Visits are planned after 3, 6, 12, 18 and 24 weeks after randomization. If additional time is needed after randomization to schedule the pulmonary rehabilitation for a patient randomized to that group, the time between visits 2 and 3 may be extended up to 6 weeks. The visit schedule will resume on the day of the first pulmonary rehabilitation visit, and all subsequent visits will be scheduled accordingly to keep the time between visits per protocol and a total 24 week treatment period.

During all the visits it is important that patients' questionnaires are completed before any other procedure. The order of the other procedures to be followed is given below as an indication but can be adapted for practical reasons.

Visit 2

- SGRQ, KBILD and UCSD SOBQ
- Adverse events and concomitant therapy assessment since last visit
- Download/review PROactive Tool and activity monitor results
- Physical examination including vital signs
- Resting SpO₂
- Blood samples for laboratory tests
- Urinary pregnancy test
- Pulmonary function test including FVC
- DL_{CO}
- Assessment of in/exclusion criteria
- Randomisation via IRT
- 6 minute walk test
- [REDACTED]
- Schedule patient for pulmonary rehabilitation if randomized to that treatment group
- Schedule Visit 3
- Send HRCT for calculation of QLF if not previously available.

Visits 3, 4, 5 and 6:

- Adverse events and concomitant therapy assessment since last visit
- Collect and download/review PROActive Tool from eDiary and activity monitor data at Visit 5
- Review pulmonary rehabilitation attendance with patient and record information from pulmonary rehabilitation reports into eCRF for patients in the PR treatment group at Visits 3, 4 and 5
- Physical examination including vital signs
- Blood samples for laboratory tests
- Urinary pregnancy test
- SGRQ, KBILD and UCSD SOBQ at Visit 5
- Pulmonary function test including FVC at Visit 5
- DLCO at Visit 5
- SP02 at Visit 5
- Six minute walk test at Visit 5
- [REDACTED]
- Instruct patient on activity monitoring and eDiary (or eDiary application for own device) and remind patient they need to pick up or will receive device in the mail to allow 7 days of use prior to next visit at Visits 4 and 6
- Schedule next visit.

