7.7 DETERMINATION OF SAMPLE SIZE

In the 1199.187 6-month data, an unadjusted mean for absolute change from baseline in 6MWT distance of 4.9 meters (sd = 76.5) was observed for nintedanib. To conservatively estimate the sample size, a standard deviation of 85.0 is used in estimation. In the 2014 Cochrane Database of Systematic Reviews [[R18-1704](#)], a mean for absolute change from baseline in 6MWT distance of 44.3 meters was observed for pulmonary rehabilitation for interstitial lung disease. The minimal clinically important difference for the 6MWD for IPF patients with combined treatment of nintedanib and pulmonary rehabilitation versus IPF patients treated with nintedanib only is 30 meters [[R18-1767](#)].

In light of the available evidence, at least 254 patients would be required to provide 80% power to detect a difference in means of 30 meters between nintedanib and pulmonary rehabilitation combination treatment versus nintedanib by itself with a two-sided type-I error of 0.05. Assuming 10% drop out, at least 141 patients per arm, or 282 patients will be required. Calculations were performed using nQuery Advisor® 6.1 statistical package by Statistical Solutions Ltd. under the fixed term test of means with two groups option for student t-test with equal variance.

Difference in Means	Common Standard Deviation	Power (%)	Total N of randomized patients
30.0	77.0	80	210
30.0	85.0	80	254

8. INFORMED CONSENT, TRIAL RECORDS, DATA PROTECTION, PUBLICATION POLICY, AND ADMINISTRATIVE STRUCTURE

The trial will be carried out in compliance with the protocol, the ethical principles laid down in the Declaration of Helsinki, in accordance with the ICH Harmonized Tripartite Guideline for Good Clinical Practice (GCP), relevant BI Standard Operating Procedures (SOPs),

Standard medical care (prophylactic, diagnostic and therapeutic procedures) remains the responsibility of the treating physician of the patient.

The investigator will inform the sponsor immediately of any urgent safety measures taken to protect the trial patients against any immediate hazard, as well as of any serious breaches of the protocol or of ICH GCP.

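### Crude adverse-event percentages by arm are tilted modestly against pulmonary rehabilitation, because only that arm can be followed for longer, and the two documents define different adverse-event windows

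*SAP*

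**What the plan says.** **Length of follow-up.** Protocol 6.2.2 plans the last visit 24 weeks after randomisation. If time is needed to schedule rehabilitation for a patient in the PR arm, "the time between visits 2 and 3 may be extended up to 6 weeks". The schedule resumes on the first PR day and later visits move with it; flow chart footnote 6 says the same. SAP 6.1 (efficacy periods) matches this: the control treatment period runs from randomisation to Visit 7, the PR period from the first PR day to Visit 7. Protocol 6.1 has no follow-up after Visit 7.

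**Adverse-event window in the SAP.** SAP 7.8.1 assigns to the treatment period "all adverse events occurring between first nintedanib intake on/after randomization till 28 days after last nintedanib intake". SAP 6.1 (safety periods) is also anchored on nintedanib intake, with no difference by arm.

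**Adverse-event window in the protocol.** Protocol 7.3.4 counts an event as on-treatment if it starts between the beginning of PR and the end of the trial. It includes all randomised patients but gives no start for controls, who have no PR. SAP 7.8 says the safety analysis is done as the protocol defines it.

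**Summary measure.** SAP 7.8.1: "All analyses of AEs will be based on the number of subjects with AEs and NOT on the number of AEs". SAP section 7 takes percentages relative to the treatment group. The SAP text gives no time at risk, no time-to-event display and no common cut-off for adverse events; SAP 7.7 summarises only the duration of PR.

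**Status.** SAP section 4 records that the trial was terminated and efficacy analysis was cut to descriptive summaries. The safety tables in SAP 7.8 remain.

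**The concern.** Patients are already on nintedanib when they enter, or have started by the day of randomisation. Under the SAP window, the weeks spent waiting for a PR place therefore count as time at risk. A control has no matching weeks, because the control's Visit 7 does not move. A percentage of patients with at least one event grows with observation time, so equal hazards produce a higher expected percentage in the PR arm for any mean delay above zero.

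Delay is plausible. PR is arranged only after randomisation, by referral to an outside facility (Protocol 4.1.1 and 6.2.2). A patient who has only just started nintedanib must have 10 days on it by the first PR day (Protocol 3.3.2).

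At stake is the side-by-side table of serious adverse events and events of special interest, which readers will use to judge whether adding PR is safe. The conflict over the window adds to this: two programmers, one following Protocol 7.3.4 and one following SAP 7.8.1, would count different events.

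**Working it through.** **The plan's own figures.** The documents give no adverse-event rate or precision target, so there is no safety figure to reproduce. The sample size concerns walk distance and reproduces (127 per arm, 254 in total, for 30 m and SD 85). It matters here only for the arm size: "will be randomised, 145 in active arm and 145 in the control group".

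**Inputs from the documents.** Control follow-up is 24 weeks from randomisation. PR follow-up is 24 + d weeks, where d is the delay to PR start. Two readings give the maximum d:
- 6 weeks are added to the schedule: d = 6, Visit 7 at 30 weeks. Footnote 6 favours this reading.
- 6 weeks is the whole Visit 2 to 3 interval: d = 6 − 3 = 3, Visit 7 at 27 weeks.

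**Assumptions.** The 24-week control risk p and the distribution of d are not given. I take p = 10%, 20% and 30%, a constant hazard equal in both arms, patients staying on nintedanib, and event collection up to each patient's own Visit 7.

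**Formula.** Weekly hazard h = −ln(1 − p)/24. Expected PR percentage = 1 − exp(−h(24 + d)) = 1 − (1 − p)^((24 + d)/24). If a share s is delayed, it is s × that value + (1 − s) × p.

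For p = 20%, d = 6: 1 − 0.8^1.25 = 24.3%. For d = 3: 1 − 0.8^1.125 = 22.2%.

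| Delay in the PR arm | Control 10% | Control 20% | Control 30% |
|---|---|---|---|
| All, 6 weeks | 12.3% | 24.3% | 36.0% |
| All, 3 weeks | 11.2% | 22.2% | 33.1% |
| Half, 6 weeks | 11.2% | 22.2% | 33.0% |
| Half, 3 weeks | 10.6% | 21.1% | 31.5% |

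**Ceiling.** The ratio of PR to control percentage approaches 30/24 = 1.25 as p falls to zero and is smaller at higher p (1.23, 1.22 and 1.20 in the first row). The relative bias therefore cannot exceed 25%.

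**Against sampling noise.** With 145 per arm and p = 20%, the standard error of a difference is √(2 × 0.2 × 0.8/145) = 4.7 points. The worst case at 20% is 4.3 points (145 × 0.0434 = 6.3 extra PR patients). With half the arm delayed 3 weeks it is 1.1 points (1.6 patients).

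**Does a time denominator remove it?** At p = 20%, h = 0.2231/24 = 0.00930 per week. Expected time to first event or end of window is 0.200/0.00930 = 21.5 weeks for controls and 0.2434/0.00930 = 26.2 weeks for PR at d = 6. Both arms then show 0.930 first events per 100 patient-weeks. Counting both arms over the same 24 weeks from randomisation also makes the expected percentages equal.

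**The case against.** The case on the other side is substantial.

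- **The larger figures are ceilings.** The extension applies only where additional time is needed. A reader might take the top row of the table as the expected bias, but it requires the whole arm to be delayed by the maximum, at an assumed risk. This stands.
- **Termination.** A reader might infer that stopping the trial made follow-up more uneven between arms. The documents give no such direction. Patients cut off at a common calendar date would have the same time since randomisation whatever their PR start, which dilutes the gap. Only patients who reached Visit 7 keep it in full, and their number is not given. This stands.
- **The protocol window.** Counting from PR start, as in Protocol 7.3.4, would take the delay out of the PR arm. That is true, but the rule has no start for controls and no window for a PR patient who never begins, and it drops events during the wait. SAP 7.8.1 is the more detailed text and says something else. This is a reason to reconcile the passages, not an answer.
- **Counting patients rather than events is usual practice.** Agreed. The defect is the absence of a common window or a time denominator.
- **No hypothesis is tested.** So no false-positive test can follow. The table will still be read arm against arm.
- **The sponsor's guideline on adverse-event presentation (SAP reference 11) may add exposure-adjusted rates.** It cannot be checked here; the SAP text does not mention them.
- **Other safety evidence.** A reader might call the serious-event table the only randomised evidence on the safety of PR. That goes too far: vital signs are summarised by plan (SAP 7.8.3), and Protocol 7.3.4 also covers physical examinations.

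**Conclusion.** The point holds in a limited form. Following SAP 7.8.1 as written gives crude percentages that, under equal hazards, are expected to be higher in the PR arm for any positive mean delay. The bias is at most 25% relative. At an assumed 20% control risk it ranges from 1.1 points (half the arm delayed 3 weeks) to 4.3 points (everyone delayed 6 weeks). This rests on a constant equal hazard and on completion of Visit 7; actual delays and event rates are not in the documents, and a calendar cut-off shrinks the gap.

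It would be wrong to conclude that the trial's tables will show a spurious harm of PR. Even the worst case at 20% is below one standard error at the planned size. The documents support a small systematic tilt in a descriptive table.

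The contradiction needs no assumption: Protocol 7.3.4 and SAP 6.1/7.8.1 define different on-treatment windows, while SAP 7.8 says the protocol is followed. The change should be made, but it does not threaten the trial's main conclusions.

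**What to change.** 1. Reconcile Protocol 7.3.4 with SAP 6.1 and 7.8.1. State in SAP 7.8.1 one adverse-event window, defined identically in both arms, and record it under SAP section 4 as a change if it departs from the protocol.
2. For serious adverse events and events of special interest, show the crude by-arm table restricted to the first 24 weeks after randomisation. Even with a 6-week delay this covers the whole 12-week programme (6 + 12 = 18 weeks).
3. Add, by arm, the patient-years at risk and the number of patients with a first event per 100 patient-years. The denominator must be time at risk within the same window used to count the events. If the nintedanib-based window is kept, time before the first intake after randomisation, and any interruption whose events are not counted, must be left out. Plain time from randomisation would not match that numerator.

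The cost is one extra table and two columns, from dates already collected. Trial conduct and sample size are unaffected.
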